6.2.8 Laboratory safety evaluations

Laboratory tests for hematology, chemistry and urinalysis are specified in *Table 2*

CONFIDENTIAL Page 33 of 61

Version: 1.0, Dated 12 September 2019

Table 2: Laboratory Tests for Hematology, Chemistry and Urinalysis

Hematology	Chemistry Panel I	Chemistry Panel II	Urinalysis	Other Lab
Hematocrit	Total bilirubin	Blood glucose	Blood	Serum β-hCG
Hemoglobina	Alkaline phosphatase	LDH	Glucose	Urine pregnancy test
Platelet count	Alanine aminotransferase	Albumin	Protein	PT
White blood cell count	Aspartate aminotransferase	Total protein	Specific gravity	INR
WBC (Total and differentials)	Urea or blood urea nitrogen ^b	Total Cholesterol	Microscopic exam ^d	
Red blood cell count	Creatinine	Triglyceride (TG)		
Absolute neutrophil count	Gamma-glutamyl transferase	LDL		
Absolute lymphocyte count	Sodium	HDL		
	Potassium	TSH		
	Calcium	T3 (Total or Free)		
	Phosphorous	T4 (free)		
	Carbon Dioxide (CO ₂) or bicarbonate ^C			
	Chloride			
	Magnesium			

^a Screening and subsequent Hb determinations should be performed before any given transfusions.

Blood drawn for these tests will be specified in informed consent form (ICF). All laboratory investigations will be performed at local laboratory.

Screening laboratory described in Table 2 will be performed, reviewed, and determined to be acceptable by the site PI/designee within \leq 14 calendar days prior to the initiation of treatment. If these initial examinations are obtained within 72 hours (or as otherwise noted) of Cycle 1 Day 1, the investigations need not be repeated. Re-screening can be done at the discretion of PI. The scan and other investigations to document measurable or evaluable disease should be performed \leq 28 days prior to initiation of treatment or as approved by the medical monitor if it is out of 28-days window period.

During screening, active HBV, HCV, HIV and CMV infection should be ruled out. To be considered negative for active infection, following algorithm will be used:

CONFIDENTIAL Page 34 of 61

^b Blood Urea Nitrogen is preferred; if not available Urea may be tested.

^C One of these tests to be performed depending on standard of care practice followed at the institution.

^d Microscopic exam, if abnormal results are noted.

Protocol No. RP6530-1901 Version: 1.0, Dated 12 September 2019

• HBV: HBc antibody should be negative or if HBc antibody is positive, HBVDNA should be undetectable

- HCV: HCV antibody should be negative or if HCV antibody is positive, HCVRNA should be undetectable
- HIV: HIV antibody should be negative. (HIV 1/2 antibody should be negative unless positive result is considered false positive by PI).
- CMV: Negative for anti-CMV IgM antibody or if positive anti-CMV IgG antibody is positive, CMV DNA should be negative. [Note: Carriers will be monitored per institutional guidelines.]

Note: Patients who show evidence of hepatitis B infection (HBsAg positive [regardless of antibody status] or HBsAg negative but anti-HBc positive), need to be evaluated for initiation of HBV antiviral prophylaxis and should be closely monitored for HBV reactivation. CMV carriers will be monitored per institutional guidelines and/or will be given anti-CMV therapy (e.g., ganciclovir, valganciclovir).

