- 13. Known seropositive requiring anti-viral therapy for hepatitis B virus (HBV) infection OR evidence of active hepatitis B infection as defined by detectable viral load if the antibody tests are positive. [Note: Subject with a positive HBcAb with an undetectable/negative hepatitis B DNA test (e.g., polymerase chain reaction [PCR] test) can be enrolled].
- 14. Known seropositive requiring anti-viral therapy for hepatitis c virus (HCV) infection OR patients with positive hepatitis C virus Ab with detectable viral load. [Note:

Version: 1.0, Dated 12 September 2019

Subject with a positive HCV with an undetectable/negative hepatitis C RNA test (e.g., PCR) can be enrolled].

- 15. Known seropositive requiring anti-viral therapy for active CMV infection (Note: A serology positive CMV subject with negative CMV PCR test will be enrolled).
- 16. Unresolved NCI-CTCAE grade 2 and above toxicity (except as mentioned in adequate organ function (Refer inclusion criteria #7) attributed to any prior therapy/procedure excluding alopecia.
- 17. Inability or unwillingness to comply with study and/or follow-up procedures outlined in the protocol;
- 18. Concurrent condition that in the investigator's opinion would jeopardize compliance with the protocol.

Note: Relapse is defined as evidence of disease progression in a patient who has previously achieved the criteria of a CR or partial remission for ≥ 6 months. Refractory disease is defined as treatment failure or as progression within 6 months from the last dose of therapy.

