Drug compliance	-	X	X	X	X	X	X	X	X	X	X	-
Safety evaluation												
AE evaluation ¹⁷	X	X	X	X	X	X	X	X	X	X	X	X
SAE evaluation	X	X	X	X	X	X	X	X	X	X	X	X
Concomitant medication	X	X	X	X	X	X	X	X	X	X	X	X

Foot notes:

- 1. Patient should be re-consented, if informed consent is obtained >30 days prior to the initiation of study drug.
- 2. Demographic profile will include age, sex and race.
- 3. Detailed history will be taken at screening that includes history of cancer, past history, no of prior therapies; prior medication (in last 4 weeks); and other medical history (history of transfusions). Any medical significant history at subsequent visit will be captured as adverse event.
- 4. Vitals will be done prior to the administration of study drug (Pre-dose) at the days specified above.
- 5. Weight will be measured at all visits. Height to be recorded at screening only; historical data is acceptable.
- 6. Physical examination will include lymph node and systemic examination. Complete physical examination will be done at screening and EOT visits. At other visits, abbreviated examination (directed physical examination) will be done depending on the assessment of tumor.
- 7. Complete blood count: hemoglobin, hematocrit, WBC (total and differential leucocyte count) and platelet count. Additional investigations will be performed if clinically indicated. Hematology should be done ≤ 14 days prior to C1D1. However, if screening assessments are performed within 72 hours of C1D1; these tests need not be repeated on C1D1.
- 8. Chemistry Panel I include total bilirubin, ALP, AST, ALT, GGT, urea/ blood urea nitrogen (BUN), creatinine, sodium, potassium, chloride, calcium, phosphorus, CO2/bicarbonate and magnesium. The tests should be done ≤ 14 days prior to C1D1. However, if screening assessments are performed within 72 hours of C1D1; these tests need not be repeated on C1D1. These tests will be performed at supplementary (unscheduled) visits if clinically indicated.

CONFIDENTIAL Page 30 of 61

Protocol No. RP6530-1901 Rhizen Pharmaceuticals SA

Version: 1.0, Dated 12 September 2019

9. Chemistry Panel II includes blood glucose, LDH, albumin, total protein, TSH, T3 (total/free), T4 (free), total Cholesterol, TG, LDL and HDL. These tests will be performed at unscheduled visits if clinically indicated.

- 10. Serology includes HIV, HBV, HCV and CMV. Historical results in last 12 weeks is acceptable.

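### The HBV screening rule clears an HBsAg-positive, anti-HBc-negative patient of active infection without an HBV DNA test

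*Protocol*

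**What the plan says.** Protocol section 6.2.8 states the aim: "During screening, active HBV, HCV, HIV and CMV infection should be ruled out". It then gives the algorithm for being considered negative. For hepatitis B: "HBV: HBc antibody should be negative or if HBc antibody is positive, HBVDNA should be undetectable".

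Exclusion 13 in section 4.2, repeated in the synopsis, has two limbs. The first is "Known seropositive requiring anti-viral therapy for hepatitis B virus (HBV) infection". The second is "evidence of active hepatitis B infection as defined by detectable viral load if the antibody tests are positive". Its bracketed note admits patients who are anti-HBc positive with a negative DNA test, so it too links the DNA test to anti-HBc.

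A note after the algorithm in 6.2.8 uses a wider definition: "Patients who show evidence of hepatitis B infection (HBsAg positive [regardless of antibody status] or HBsAg negative but anti-HBc positive". It asks that these patients be assessed for antiviral prophylaxis and watched closely for reactivation. It does not ask for HBV DNA before entry.

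Table 1 (section 6.1), footnote 10, reads "Serology includes HIV, HBV, HCV and CMV. Historical results in last 12 weeks is acceptable". It names no individual HBV marker and does not list HBV DNA.

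**The concern.** The protocol defines active hepatitis B by viral load, but it asks for a viral load only when an antibody is positive. HBsAg is an antigen, so a positive HBsAg does not meet that condition. One group of patients therefore counts as showing evidence of infection under the note and as negative for active infection under the algorithm, with no viral load measured.

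The setting adds weight:

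- Section 3.5.5 describes CLL patients as being at raised risk of infection through impaired immunity.
- Section 1.2 names the liver as a target organ, and section 1.3 lists Grade 3 transaminitis among the dose-limiting toxicities.
- Table 5 (section 7.7) treats transaminitis with prednisone and, for Grade 3 events that do not respond, mycophenolate. It includes no HBV DNA check.
- Section 7.2 presumes that a toxicity is drug-related unless there is a clear alternative explanation.

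It is an inference from these sections, not a statement in the protocol, that a patient admitted with unmeasured viraemia could be given immunosuppression for a liver signal, and that a hepatitis flare could be attributed to Tenalisib.

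**Working it through.** The plan states no figure on this point, so there is none to reproduce. The check is a truth table, followed by a scale calculation on an assumed frequency.

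**Step 1: apply the rules as written.** The inputs are the algorithm and note in section 6.2.8 and the second limb of exclusion 13, with the antibody taken as anti-HBc, the only one that 6.2.8 names for HBV.

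| HBsAg | anti-HBc | Evidence of infection (6.2.8 note) | DNA called for (6.2.8 algorithm) | Result if DNA is in fact detectable |
|---|---|---|---|---|
| + | + | yes | yes | not negative; excluded |
| + | − | **yes** | **no** | **classed as negative; second limb not triggered** |
| − | + | yes | yes | not negative; excluded |
| − | − | no | no | classed as negative |

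The note recognises 3 of 4 patterns as evidence of infection and the algorithm calls for DNA in 2 of 4. The difference, 3 − 2 = 1, is the HBsAg-positive, anti-HBc-negative pattern.

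**Step 2: apply the proposed rule (DNA if either marker is positive).** Over the eight combinations of HBsAg, anti-HBc and DNA, one classification changes: HBsAg positive, anti-HBc negative, DNA detectable moves from negative to not negative. With DNA undetectable the same serological pattern still passes, now after a test. The other six combinations are untouched.

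**Step 3: scale.** The documents do not give the frequency p of the pattern. *Assumption:* p between 0.1% and 1% of patients, independent between patients. The chance of at least one among n is 1 − (1 − p)^n and the expected number is n × p. The sample sizes are n = 61 (planned maximum, protocol section 9.2) and n = 21 (enrolled, SAP section 6).

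| p (assumed) | n = 61: chance of at least one | n = 61: expected | n = 21: chance of at least one | n = 21: expected |
|---|---|---|---|---|
| 0.1% | 1 − 0.999^61 = 5.9% | 0.06 | 1 − 0.999^21 = 2.1% | 0.02 |
| 0.5% | 1 − 0.995^61 = 26.3% | 0.31 | 1 − 0.995^21 = 10.0% | 0.11 |
| 1% | 1 − 0.99^61 = 45.8% | 0.61 | 1 − 0.99^21 = 19.0% | 0.21 |

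These are chances of meeting the serological pattern. The harm also needs detectable DNA in that patient, so under the same assumption they are upper bounds on the chance of enrolling a viraemic patient through this gap.

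**The case against.** The strongest reply is that other provisions catch this patient.

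- **Exclusion 13, first limb.** It carries no antibody condition, and section 5.2 says that chronic HBV carriers should receive prophylactic antivirals. If prophylaxis counts as requiring antiviral therapy, a recognised carrier is already excluded. That reading is possible but not the natural one: section 5.2 and the note in 6.2.8 both provide for carriers on study under prophylaxis and monitoring. The first limb also names no test and reaches only patients already known to be seropositive.
- **Plural antibody tests in exclusion 13.** Another positive HBV antibody might trigger the second limb. The tests are not defined, however, and 6.2.8 names anti-HBc alone.
- **Discretionary routes.** Section 6.1 allows extra testing for safety and mentions HBV, and exclusions 5 and 18 rest on investigator judgement. None of these requires a DNA test.
- **Liver safeguards.** Entry limits on ALT and AST and liver chemistry at each treatment visit reduce the risk, but they do not measure viral load.

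Part of the reply stands. Once an HBsAg result is in hand the note makes the patient visible to the site, so what is missing is a mandated DNA test at entry, not recognition of the result. The assumed frequencies have no basis in the documents, and one pattern in four is a count of table rows, not a rate. The SAP also records that stage 2 will not start, so a change can no longer affect enrolment in this trial.

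**Conclusion.** The concern holds. As written, the section 6.2.8 algorithm and the second limb of exclusion 13 class an HBsAg-positive, anti-HBc-negative patient as free of active hepatitis B with no DNA result, and no other provision requires one. This conclusion rests on the text alone and does not depend on the assumed frequencies.

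The gap is narrow: every anti-HBc-positive patient must already have undetectable DNA. Even at the top of the assumed range fewer than one such patient would be expected among 61. It is a patient-safety weakness in an eligibility rule that should be corrected. The two-stage design and the response analyses are not affected.

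**What to change.** In section 6.2.8, in exclusion 13 and in the synopsis copy of that exclusion, require both HBsAg and anti-HBc at screening, and undetectable HBV DNA if either is positive. Name the two markers in footnote 10 of Table 1. As a clarification, state in exclusion 13 that prophylaxis in a DNA-negative patient does not count as requiring antiviral therapy, which settles how its first limb should be read.

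HBV serology and HBV DNA are already in the plan. The cost is the wording change and one DNA test per HBsAg-positive, anti-HBc-negative patient.

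Because enrolment has ended, the correction mainly matters for the record and for any later protocol that reuses the rule. For the 21 patients enrolled, the baseline serology listing planned in SAP section 12 can be checked for this pattern, provided HBsAg was collected.

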5.2 Concomitant Medications

In general, patients should not to take any concomitant medications during the study, unless it is required as a standard of care (as necessary supportive care), prophylaxis or for the treatment of adverse event in the opinion of the treating investigator. The following guidance should be followed for concomitant medications and the information including blood transfusion should be recorded in CRF.

 Antimicrobial and/or anti-viral prophylaxis should be used according to local standard practice; PJP and herpes zoster prophylaxis is strongly recommended. CMV carriers will be monitored per institutional guidelines and/or will be given anti-CMV therapy (e.g.,

Version: 1.0, Dated 12 September 2019

- ganciclovir, valganciclovir). Similarly, chronic carriers of HBV should receive prophylactic anti-viral therapy.
- G-CSF and other hematopoietic growth factors may be used for the management of acute toxicity (such as febrile neutropenia) when clinically indicated.
- Transfusions (blood/platelets) may be given, based on standard criteria and clinical judgment.
- No routine prophylactic anti-emetics or pre-medications should be given outside of protocol requirements. However, these medications may be administered for the treatment of symptoms.
- Patient may receive prophylactic allopurinol, in case the risk of tumor lysis syndrome.
- Low doses of steroids are allowed if it administered at dose ≤ 20 mg per day of prednisone or equivalent. The dose should be stabilized for at least 1 week or 5 halflives (whichever is shorter) prior to C1D1.
- Patients are permitted to use of topical, ocular, intra-articular, intranasal, and inhaled corticosteroids (with minimal systemic absorption).
- Inactivated seasonal influenza vaccine can be given to subjects before treatment and while on therapy without restriction.
- If concomitant treatment of drugs metabolized by CYP3A4/CYP2C9 enzymes are clinically warranted, careful observation of the patient is advised.
- Low molecular weight heparin (LMWH), Dabigatran or Edoxaban is acceptable for prophylaxis and/or treatment of venous thrombosis.

5.3 **Prohibited Medications**

The following treatments are prohibited while on the clinical trial and should be discontinued:

- Any other anti- leukemia/lymphoma therapy
- Herbal medications. Patients should stop using herbal medications at least 7 days prior to C1D1.

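### The CMV screening rule in Protocol 6.2.8 gives different answers for some IgM/IgG/DNA results and does not match exclusion 15

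*Protocol*

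**What the plan says.** Protocol section 6.2.8 sets the aim: "During screening, active HBV, HCV, HIV and CMV infection should be ruled out". It then makes a list of rules the operative test of who is negative for active infection ("following algorithm will be used"). The three rules that matter here are:

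- The hepatitis B rule, with one antibody in both branches: "HBc antibody should be negative or if HBc antibody is positive, HBVDNA should be undetectable"
- The hepatitis C rule, which has the same form, with its own antibody in both branches and viral RNA as the second test.
- The CMV rule, which changes antibody between branches: "Negative for anti-CMV IgM antibody or if positive anti-CMV IgG antibody is positive, CMV DNA should be negative"

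Exclusion 15, in the synopsis and in section 4.2, reads: "Known seropositive requiring anti-viral therapy for active CMV infection (Note: A serology positive CMV subject with negative CMV PCR test will be enrolled". Exclusions 13 (HBV) and 14 (HCV) have a similar opening, but each adds a separate criterion that excludes an antibody-positive patient with detectable virus. Exclusion 15 has no such criterion.

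Exclusion 5 removes patients with ongoing severe systemic infection, viral infection included, as judged by the investigator.

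**The concern.** The HBV and HCV rules each name one antibody in both branches, so a negative antibody settles the matter and a positive one sends the patient to a nucleic-acid test. The CMV rule names IgM in the first branch and IgG in the second, and its second branch uses the word positive twice in a way that does not parse. The two branches therefore do not divide patients into separate groups. One serology pattern falls under both and another under neither.

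Two things are at stake. The first is consistent entry: two sites holding the same results could decide differently, on an infection that Protocol section 3.5.5 lists among the risks for these patients. The second is the classification of deviations. SAP section 7.2 gives enrolment against the inclusion or exclusion criteria as an example of a major deviation, and major deviations remove a patient from the per-protocol set. A patient who fails 6.2.8 but meets no item in 4.2 could be classified either way.

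**Working it through.** The plan states no figure on this point. The check is a truth table of the rule as printed.

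**Inputs.** IgM, IgG and CMV DNA are each negative (−) or positive (+), which gives 2 × 2 × 2 = 8 combinations. The rule is in Protocol 6.2.8; the Note and the exclusion are in Protocol 4.2, item 15.

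**Readings.** A patient counts as negative for active infection if:

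- A (literal, either branch suffices): IgM−, or IgG+ with DNA−.
- B (the second branch governs whenever IgG is positive): DNA− if IgG+; IgM− if IgG−.
- C (built like the HBV and HCV rules, with the first positive referring to IgM): IgM−, or DNA−.
- D (what the exclusion 15 Note implies): both antibodies negative, or DNA−.

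| IgM | IgG | DNA | A | B | C | D |
|---|---|---|---|---|---|---|
| − | − | − | clear | clear | clear | clear |
| − | − | + | clear | clear | clear | clear |
| − | + | − | clear | clear | clear | clear |
| − | + | + | **clear** | **not** | **clear** | **not** |
| + | − | − | **not** | **not** | **clear** | **clear** |
| + | − | + | not | not | not | not |
| + | + | − | clear | clear | clear | clear |
| + | + | + | not | not | not | not |

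Six of the eight rows agree on every reading. Two do not.

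1. **IgM−, IgG+, DNA+.** A and C clear the patient; B and D do not. The same split arises before any DNA result exists: A and C clear the patient on IgM alone, while B and D wait for the DNA test. Table 1 footnote 10 lists only serology for CMV, and Table 2 lists no CMV DNA test, so the schedule does not settle when one is needed.
2. **IgM+, IgG−, DNA−.** On A or B the patient meets neither branch and is not counted as negative. The Note to exclusion 15 says that a serology-positive patient with a negative PCR is enrolled.

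In the second row of the table (both antibodies negative, DNA positive) no reading calls for a DNA test. The readings agree, so it is not counted as a conflict.

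**Exclusion 15 taken alone.** It excludes a patient who is seropositive and requires therapy for active infection. If therapy is not judged to be required, it removes 0 of the 8 combinations. Its Note says who enters (PCR-negative) and leaves the PCR-positive patient to inference. In exclusions 13 and 14 the corresponding exclusion is written out.

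**When a patient in the first split row could enter.** All of these must hold: the site follows reading A or C; the patient is not judged to require anti-viral therapy (exclusion 15); the patient is not judged to have severe systemic infection (exclusion 5); and the site does not treat the Note as a bar.

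**The case against.** The strongest reply is that the intent is clear. Section 6.2.8 says that active CMV infection is to be ruled out, its second branch asks for negative DNA when IgG is positive, and the Note admits the PCR-negative patient, which implies that the PCR-positive one stays out. Much of this stands. A reader might infer that the missing viral-load criterion settles that viraemic patients can be entered. The documents do not support that: entry is possible only on some readings and under the conditions listed above.

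A reader might also say that the rule is silent on the IgM-positive, IgG-negative patient. It is not. The rule defines who counts as negative, so meeting neither branch is an answer. The defect is that this answer conflicts with the Note when PCR is negative.

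Three further inferences fail:

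- **Counting every CMV carrier among the planned 61 as affected.** The documents give no prevalence of CMV antibodies, a DNA-negative carrier with either IgM result is cleared on every reading, and SAP section 6 reports 21 patients enrolled with Stage 2 not to be initiated.
- **Setting section 5.2 against exclusion 15.** Section 5.2 says "CMV carriers will be monitored per institutional guidelines and/or will be given anti-CMV therapy". That concerns carriers on study, whereas exclusion 15 concerns patients who need therapy for active infection at entry.
- **Setting Table 1 footnote 10 against 6.2.8.** The footnote says "Historical results in last 12 weeks is acceptable" of serology. Section 6.2.8 sets no 28-day age limit for serology, so an older result can inform a screening decision.

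Finally, the point changes no endpoint, sample size or error rate, and enrolment is over. That limits its reach but does not make the rule consistent.

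**Conclusion.** The point holds as an inconsistency in a stated eligibility rule, in three parts. Section 6.2.8 gives two answers for an IgM-negative, IgG-positive patient whose DNA is positive or untested. It conflicts with the exclusion 15 Note for an IgM-positive, IgG-negative, DNA-negative patient. Exclusion 15 lacks the express viral-load criterion of exclusions 13 and 14, so the Note only implies a bar on PCR-positive patients. Taken literally, the rule can clear a DNA-positive patient despite the instruction to rule out active infection.

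The size is two of eight combinations. How many of the 21 enrolled patients fell into them cannot be derived from the documents. The count of two rests on treating readings A to D as the possible ones; conflict 1 needs only A and B, and conflict 2 only the literal text and the Note. For this closed study, the practical effect is on how deviations are classified and on any later protocol that reuses the wording.

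**What to change.** Reconcile section 6.2.8 with exclusion 15, in both the synopsis and section 4.2, so that each IgM/IgG/DNA combination leads to one and the same outcome in all three places. State when a CMV DNA result is needed before entry, and whether a PCR-positive patient is excluded. The sponsor's medical expert decides the clinical content; this review takes no position on it.

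For the patients already enrolled, record which reading was applied when deviations are categorised under SAP sections 7.2 and 11.

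The change is to wording only. Its cost is that some carriers may need the PCR that the protocol already names.
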